- 7. Nonadherence, as determined by a trough level less than 7 ng/mL after achieving therapeutic level with no other rationale for sub-therapeutic levels.
- 8. Adults unable to consent
- 9. Pregnant women
- 10. Prisoners

5) Study Timelines

Expected date of data collection and analysis completion by July 2019.

The duration of an individual subject's participation in the study is 6-8 weeks from initial study enrollment.

The enrollment period is expected to occur from IRB approval through December 2018, or until 60 subjects have been enrolled into to the study.

6) Study Endpoints

Primary Endpoints: Change in neurocognitive side effects assessed by MOCA scale, Digit symbol substitution test and tremor assessment scale.

[figure not shown]
Secondary Endpoints: Change in self-reported side effects, tacrolimus dose over concentration ratio, graft survival and patient survival.

Page :

7) Procedures Involved

Single-center, prospective, open-label, randomized study to evaluate the difference in neurocognitive side effects of Envarsus versus immediate release tacrolimus.

Figure 1. Flow diagram of study design

Enrollment:

- 1. Rolling enrollment of patients 65 years or older that fit the inclusion criteria outlined above
- 2. Plan to enroll 30 patients to each arm
- 3. Anticipated enrollment rate:
 - a. 6-8 patients in first month
 - b. 10 patients per month thereafter
 - c. Until total of 60 patients have enrolled
 - d. If any patients were to withdraw or be dropped from the study prior to completion of follow up testing, we will try to enroll more patients to replace them

Protocol:

- 1. Potential study participants will be screened within 4 weeks after transplantation.
 - Patients who meet study criteria will be consented and enrolled by 8 weeks posttransplantation
- Patients who consent to the study will be administered a baseline panel of neurocognitive tests.
 (Of note, these tests are not regularly administered to our post-transplant patients and are not part of the standard of care.)

Page 4

- Tests include: the MOCA, digit symbol substitution test, tremor assessment.
- They will also answer a side effects questionnaire.
- These tests will be performed in the mornings, between 1-4 hours after patients' morning tacrolimus dose administration.
- 3. Subjects who enroll will then be randomized to either remain on IR tacrolimus (current standard of care) or be converted to Envarsus.

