 - Those randomized to Envarsus will begin conversion immediately based on a dosing ratio of 0.8 x the total 24-hour IR tacrolimus dose that will lead to therapeutic tacrolimus trough levels.
 - Therapeutic drug level monitoring and will occur as per usual standard of care for all patients.
 - Blood draws for all subjects will occur as per usual standard of care and will be managed as per usual by the patients' post-transplant team.
 - Envarsus to be supplied by the pharmaceutical company.
 - IR tacrolimus to be supplied by patient's insurance
 - Any applicable vital signs or labs if collected as patient's standard of care may be used during the study period for study purposes.
- 4. Subjects' tacrolimus levels will be monitored and titrated as per usual practice at our center.
 - The target tacrolimus trough is 8-14ng/mL for patients within the first 3 months of transplantation.
 - They will obtain labs per standard of care (weekly) or at provider discretion.
 - Tacrolimus dose adjustment will be made per clinical judgement and expected to reach target goal range within 2 blood draws one week apart. (Total of two weeks).
- 5. 6 weeks after study enrollment (+/- 5 days), subjects will be administered the same panel of neurocognitive testing and self-reported questionnaires as at baseline.
 - The tests will be performed in the mornings, between 1-4 hours after patients' morning tacrolimus dose administration.
 - At this appointment the patients will receive a \$20 check to help with travel expenses for additional appointments.
- 6. After this study period, subjects who were randomized into the Envarsus arm will be given the option to remain on Envarsus or return to IR tacrolimus. Those who remain on Envarsus will be part of the extension phase of this study. The funding for the patients' Envarsus at this phase would revert back to their insurance coverage, with potential for coverage by Veloxis if further study will be completed (see below).
- 7. The extension phase of this study will create a cohort for the assessment of long term graft and patient outcomes.
 - We anticipate that if sufficient numbers plan to remain on Envarsus, we can apply for further funding for this phase. If further funding is approved, we will seek another IRB approval for continuation of this study.

 We do not anticipate long-term data to be collected about subjects beyond their period of participation in this study.

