encrypted online data management system (REDCap) using password protected computers. Due to the nature of the study, we will need to include patient identifiers in the database in order to assess adverse events for the duration of the study. The data will be stored until 1 year after publication of the study.

Data analysis plan: We will compare the neurocognitive scores between the Envarsus and IR Tacrolimus arms of the study. Sample size calcuation was done to determine sample size needed to detect a 1 point difference for each neurocognitive test we plan to use. The two groups will be compared using two-sample mean comparison via t test.

We will not be collecting or banking any patient specimens for this study.

9) Data and/or Specimen Banking

Participant data will be stored for potential future use by the PI and co-PIs pending further IRB approval. Data will only be released upon approval of PI with IRB approval. Data will be stored on encrypted devices requiring password protection. Passwords will not be shared by any users. Paper records of patient testing will be stored in locked cabinets with access only by research staff.

10) Provisions to Monitor the Data to Ensure the Safety of Subjects

Data will be extracted from the EMR and stored in a password protected folder on a secure, encrypted network. This network is only accessible by staff at UC Davis Health. This password protected folder will only be authorized to be accessed by study personnel. When this data is removed from this folder such as for the purposes of data analysis, each patient's data will be coded with a de-identified number. The identified patient information stored in the protected file will be destroyed at the end of this study.

For the duration of a subject's participation in the study, their clinical events and laboratory values will be monitored for any adverse events, including acute rejection, surgical complication, infections, cardiovascular events, neurologic events, and other events or side effects that may potentially be related to IR tacrolimus or Envarsus therapy. These data will be reviewed by the PI and co-PIs to determine if they are the direct result of use of the investigational drug.

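### The tacrolimus dose/concentration endpoint has no stated scale, time point or analysis; comparing log(D/C) with the subject's own baseline as covariate would be more powerful and would not depend on which way up the ratio is written

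*Combined protocol and SAP*

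**What the plan says.** Section 6 names the endpoint in a list: "Secondary Endpoints: Change in self-reported side effects, tacrolimus dose over concentration ratio, graft survival and patient survival". Section 2 has much the same list. Neither says which dose, which concentration or which time point, nor whether the week-6 value or a change is meant.

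The analysis plan is a short paragraph in Section 8. It opens with "We will compare the neurocognitive scores between the Envarsus and IR Tacrolimus arms of the study", gives a sample-size basis in terms of the neurocognitive tests, and ends with "The two groups will be compared using two-sample mean comparison via t test". No log scale, ratio of means or baseline adjustment appears anywhere.

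Section 7 bears on how the ratio will behave. Subjects assigned to Envarsus convert "based on a dosing ratio of 0.8 x the total 24-hour IR tacrolimus dose that will lead to therapeutic tacrolimus trough levels". It also states "The target tacrolimus trough is 8-14ng/mL for patients within the first 3 months of transplantation", with no distinction between arms, and then "Tacrolimus dose adjustment will be made per clinical judgement". The size is "Plan to enroll 30 patients to each arm". All subjects are on IR tacrolimus at entry and must have reached a therapeutic level (Section 4), and routine labs are normally weekly (Section 7, step 4).

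**The concern.** A ratio of two positive quantities is usually skewed, and formulation effects on it are usually thought of as proportional. A t test on raw means has two weaknesses for such an endpoint.

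- **It ignores the baseline.** Dose requirement differs between people. Each subject's own D/C on IR tacrolimus should be obtainable before randomisation and would remove part of that variation.
- **It is not invariant to inversion.** D/C and C/D carry the same information, but their raw means do not, so the two t tests can give different answers. With nothing fixed in advance, that choice stays open until the data are seen.

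At stake is how precisely the trial can describe the dose requirement on Envarsus relative to IR tacrolimus in recipients aged 65 or more. The primary endpoint is not affected.

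**Working it through.** **The plan's own figure.** None exists for this endpoint. The 30 per arm refers to a 1-point difference on each neurocognitive test and cannot be reproduced, because no SD, alpha or power is given.

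**Inputs**
- From the documents: 30 per arm; conversion factor 0.8.
- Assumed: true week-6 ratio of geometric means 0.8; two-sided 5%; lognormal D/C with the same log SD σ at baseline and week 6 and correlation ρ between them; a complete baseline and week-6 value for all 60 subjects. Ranges: σ 0.3-0.6, ρ 0.5-0.8.

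**When 0.8 carries over to D/C.** If the dose falls to 0.8 and the trough is held, D/C is multiplied by 0.8/1 = 0.8. If the trough also falls to 0.8, D/C is multiplied by 0.8/0.8 = 1. So 0.8 is a planning value that holds only if troughs are maintained.

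**Log-scale formulas.** The effect is |ln 0.8| = 0.223 and √(2/30) = 0.258. Noncentrality is 0.223 / (s × 0.258), where s is:
- week-6 value only: σ
- change from baseline: σ√(2(1−ρ))
- baseline as covariate (ANCOVA): σ√(1−ρ²)

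At σ = 0.5 and ρ = 0.8:
- week 6 only: s = 0.50, noncentrality 1.73, power 40%
- change: s = 0.5 × √0.4 = 0.316, noncentrality 2.73, power 77%
- ANCOVA: s = 0.5 × 0.6 = 0.30, noncentrality 2.88, power 81%

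At ρ = 0.5 the change score has s = σ, so it gains nothing over the week-6 value. ANCOVA has s = 0.866σ and still gains.

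**Simulation for all methods** (20,000 trials per setting; power in %; the last column is the share of trials in which week-6 raw D/C and raw C/D t tests disagree on significance):

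| σ / ρ | Raw wk 6 | Log wk 6 | Raw change | Log change | Raw ANCOVA | Log ANCOVA | Disagree |
|---|---|---|---|---|---|---|---|
| 0.3 / 0.5 | 79 | 81 | 73 | 81 | 88 | 90 | 9 |
| 0.4 / 0.7 | 53 | 57 | 67 | 78 | 79 | 84 | 16 |
| 0.5 / 0.5 | 37 | 40 | 31 | 41 | 44 | 50 | 18 |
| 0.5 / 0.8 | 36 | 40 | 62 | 77 | 73 | 81 | 18 |
| 0.6 / 0.8 | 26 | 30 | 44 | 61 | 54 | 65 | 18 |

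The log columns agree with the formulas. Separate runs of 4,000 trials agree within about 2 points. With no true difference, every method rejects in about 5% of trials. At a CV of 30% (log SD just under 0.3), a separate run gave 8% disagreement.

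**Splitting the gain**
- Scale alone, week 6: about 1-4 points.
- Scale alone, within ANCOVA: about 2-11 points.
- Baseline: at 0.5 / 0.8, raw ANCOVA already moves power from 36% to 73%, which is 37 of the 45 points gained by log ANCOVA (81 − 36).
- Raw change to log ANCOVA: about 17-21 points in these five settings.
- Limit: at σ = 0.3 and ρ = 0.8, raw change already has 98% power and log ANCOVA over 99%, so the choice hardly matters.

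**Inversion.** log(C/D) = −log(D/C), so on the log scale both directions give the same p value.

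**The case against.** The strongest reply is that the plan never applies the t test to this endpoint. The sentence closes a paragraph about neurocognitive scores, so it may not cover D/C at all. That stands, and it is why the point is put as a missing definition and analysis, with the t test considered only as what would follow if it were applied. Either reading leaves the same gap.

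Second, the words about change at the head of the endpoint list may also govern the ratio, in which case the baseline is used. This reading is possible. The raw week-6 comparison would then be the wrong comparator and raw change the right one; the table gives both.

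Third, the power figures depend on assumed variability. They do. At σ = 0.3 even the raw week-6 test has about 79% power.

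A reader might also infer more than the documents support:
- **That the raw scale by itself costs much of the power.** At week 6 it costs about 1-4 points.
- **That the 0.8 rule makes changes in D/C unequal by construction.** The rule acts on dose. D/C follows only if troughs are held, and titration by clinical judgement comes afterwards.
- **That this endpoint is the trial's only check on 0.8.** Section 10 compares sub-therapeutic troughs between arms at half enrolment, and troughs are monitored throughout. Testing 0.8 is not a stated objective.

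**Conclusion.** The point holds as an inexpensive improvement to one secondary endpoint. D/C has no stated scale, time point or analysis, and the one named method would be a weak choice for it. Under the assumptions above, log ANCOVA raises power over a raw week-6 t test by about 45 points at σ 0.5 and ρ 0.8, 13 points at 0.5 and 0.5, and 11 points at 0.3 and 0.5. Most of that comes from the baseline. The log scale adds a smaller amount and removes the roughly 8-18% of trials in which week-6 D/C and C/D disagree on significance.

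Type I error is not at issue for any single analysis fixed in advance. The 0.8 is a starting conversion ratio followed by titration, so the estimated ratio can be shown beside it but is not fixed by it. The sizes would change with the real SD and correlation, which the documents do not give. The ordering, with log ANCOVA at least as powerful as the alternatives, held in every setting tested.

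**What to change.** Add one sentence to Section 6: the endpoint is D/C at week 6, defined as total 24-hour tacrolimus dose divided by trough concentration. Use the routine trough nearest the week-6 visit and the dose in force when it was drawn. The neurocognitive tests are timed 1-4 hours after the morning dose, so a sample taken at that session would not be a trough.

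Add one sentence to the data analysis plan: compare arms on log(D/C) by ANCOVA, with the subject's own log(D/C) from the last trough on IR tacrolimus before randomisation as covariate, and report the ratio of geometric means (Envarsus to IR) with a 95% CI. The starting factor of 0.8 may be shown alongside for reference.

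Adjustment is preferable to a log change score, which gains almost nothing at correlation 0.5 (41% against 40% for log week 6 alone, compared with 50% for ANCOVA).

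The cost is two sentences. No visit, assay or dosing rule changes, because doses and troughs are already part of routine care. The result is reported as a ratio in place of a mean difference, and a rule is needed for any subject without a usable baseline or week-6 trough.

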In particular, neurologic toxicities such as tremor, headaches, confusion and neuropathy are common side effects of Tacrolimus immediate release³. When used in combination with mycophenolate mofetil, a common immunosuppressant regimen, the incidences of these adverse effects are significant⁴. Per Prograf ® package insert, about one-third of patients experience tremors and one-fourth of patients experience headaches⁴. These neurologic side effects may impose profound limitations on patients' daily activities and quality of life. These studies were conducted in the general population with an average age of 48 years (range 17-77 years). Elderly patients tend to be more sensitive to medications, both the intended effects and the toxicities. The elderly patient experiences changes in organ function and body composition, leading to effects on drug metabolism and disposition⁵. Studies have demonstrated that elderly patients achieve higher trough drug levels even when normalizing for patient weight and dosage⁶. In addition, elderly patients tend to have more co-morbidities and are more vulnerable to polypharmacy, leading to more potential drug interactions. All of these factors combined may increase the likelihood and severity of toxicities experienced by the elderly patient.

Page 1

HRP-503-PTOTOCOL TEMPLATE-General

Template Revision: June 15, 2017

University of California, Davis Health, is the leading renal transplant center in the nation. In 2016 alone, over 400 renal transplants were performed. Of those, 72 transplants were in patients age 65 years or greater. With about one-fourth of our transplants performed in the elderly patient population there is great opportunity to improve outcomes in this patient population. The UC Davis Health renal transplant patient population is very diverse, with no one ethnicity claiming majority. Between May 2016 and July 2017, 30% of transplant recipients self-identified as white, 11% as black, 29% as Hispanic, 26% as Asian and 4% as other. As a large academic institution, UC Davis Health is well equipped to successfully manage research projects and see them to completion. With a dedicated office for research within our campus, research coordinators, biostatisticians and other research services available ensures research that is conducted at UC Davis Health is robust and valuable to our patients as well as to the broader health care audience.

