Note: Envarsus is approved by the FDA for use in kidney transplant patients for prevention of rejection.

Below are the neurocognitive tests that we will perform on each patient. These tests will be administered by clinical research coordinators, who will be trained on how to complete each test in order to achieve standardized testing practice.

- 1. Montreal Cognitive Assessment (MOCA) Test
 - a. Available as a paper test or an app (See attachment)
 - b. Well researched and accepted in the literature as a measure of mild to moderate cognitive impairment^{8,9}
 - c. MOCA test version 7.1 will be administered at Day 0, MOCA test version 7.2 will be administered at final 6-week visit.
- 2. Digit Symbol Substitution (DSS) Test
 - a. Available as a paper test or an app (See attachment)
 - b. Instrument to measure memory and processing speed¹⁰
- 3. Tremor Assessment:
 - a. Patient Global Impression of Change Scale (PGI)
 - b. Clinicial Global Impression of Improvement (CGI)
 - c. Both are 7-point scales assessing tremor change. Both were used in STRATO.⁷

Below is the self-reported assessment we will use on each patient:

- 1. The Organ Transplant Symptom and Wellbeing Instrument (OTSWI).
- 2. Quality of Life in Essential Tremor Questionnaire (QUEST).

References

- 9. Tiffin-Richards, Frances E., et al. "The Montreal Cognitive Assessment (MoCA)-A Sensitive Screening Instrument for Detecting Cognitive Impairment in Chronic Hemodialysis Patients." PloS one 9.10 (2014): e106700.
- 10. Hoyer, W. J., Stawski, R. S., Wasylyshyn, C., & Verhaeghen, P. (2004). Adult age and digit symbol substitution performance: a meta-analysis. Psychology and aging, 19(1), 211.

8) Data and/or Specimen Management and Confidentiality

All individuals with access to participant information will be HIPAA trained and data will be stored using password protected computers and accounts. Data will be stored via a secured,

Page 6

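### The week-6 assessor is not masked and the CGI rater is not named, so assessor expectation could bias the CGI and the administration and scoring of MOCA and DSS

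*Combined protocol and SAP*

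**What the plan says.** Section 7 (Procedures Involved) describes a "Single-center, prospective, open-label, randomized study". Section 6 gives the primary endpoint as "Change in neurocognitive side effects assessed by MOCA scale, Digit symbol substitution test and tremor assessment scale". Section 7 breaks the tremor assessment into two scales, a patient global impression (PGI) and a clinician global impression (CGI), and adds: "Both are 7-point scales assessing tremor change".

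On who does the testing, Section 7 says: "These tests will be administered by clinical research coordinators, who will be trained on how to complete each test". The stated purpose of the training is standardised testing. No sentence in the protocol masks an assessor to treatment arm, and none says who assigns the CGI score.

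The order of events is clear. Baseline testing comes first, randomisation follows, conversion starts at once in the Envarsus arm, and the same panel is repeated 6 weeks after enrolment (within 5 days either way). Levels and doses are managed by the usual post-transplant team. The analysis, in Section 8 under the data analysis plan, is a two-sample t test between arms.

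**The concern.** Open-label treatment does not require open-label assessment. At week 6, whoever gives the MOCA and DSS, and whoever scores the CGI, may know which drug the patient takes. Section 3 (Background) states a directional hypothesis, that conversion to Envarsus will reduce toxicity. If expectation affects the assessor, it would plausibly favour Envarsus, although the documents contain no measurement of this.

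The outcomes differ in exposure. The CGI is a judgement of change, so it is the most exposed of the observer-dependent measures, and it has neither a named nor a masked rater. MOCA and DSS are performance tests, where the examiner acts through prompting, timing and scoring. At stake is how a positive primary result would be read: a difference between arms could be put down to assessor expectation, and no later analysis of the same data could settle the question.

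**Working it through.** **1. Where knowledge of the arm can act.** Section 7 places baseline testing before randomisation, so the assessor cannot know the arm at baseline. The exposure is confined to the single week-6 visit.

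**2. Which measures a masked assessor would protect.**

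| Measure | Role | Who produces the score, per protocol | Would a masked assessor help? |
|---|---|---|---|
| CGI | Primary (tremor) | Not named | Yes, if the rater is masked |
| MOCA, DSS | Primary | Administered by coordinators; scorer not stated | Yes for administration and scoring; no for patient expectation or effort |
| PGI | Primary (tremor) | The patient, who knows the arm | No |
| OTSWI, QUEST | Self-reported | The patient, who knows the arm | No |

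**3. The plan's own figure.** Section 8 says that the sample size was set to detect a 1-point difference on each test, and Section 7 plans 30 per arm. SD, alpha, sidedness and power are not stated for this calculation, so the 30 cannot be reproduced. Solving backwards under a normal approximation with two-sided 5% and 80% power (both assumed): SD = 1 / [(1.960 + 0.842) × √(2/30)] = 1.38 points.

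**4. False-positive rate under an assumed bias.** Take no true drug effect and a systematic shift of d SD between arms. With n = 30 per arm, df = 58, two-sided 5% (assumed; critical value 2.002), the noncentrality is λ = d × √(n/2) = d × √15 = 3.873d. The rejection probability is P(T > 2.002) + P(T < −2.002) for a noncentral t with 58 df.

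| Assumed shift | λ | False-positive rate | Of which favouring the direction of the shift |
|---|---|---|---|
| 0 | 0 | 5.0% | 2.5% |
| 0.2 SD | 0.77 | 11.9% | 11.5% |
| 0.3 SD | 1.16 | 20.8% | 20.7% |
| 0.5 SD | 1.94 | 47.8% | 47.8% |

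**5. The same check in points (normal approximation).** With SE = SD × √(2/30), the rate is Φ(b/SE − 1.96) + Φ(−b/SE − 1.96). For SD 1.38, SE = 0.356.

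| Assumed SD (points) | Shift 0.25 point | Shift 0.5 point |
|---|---|---|
| 1 | 16% | 49% |
| 1.38 | 11% | 29% |
| 2 | 8% | 16% |
| 3 | 6% | 10% |

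A shift of half the 1-point target therefore gives 10% to 49% over this assumed SD range. Every bias size and SD here is an assumption. The tables show sensitivity and do not estimate the bias in this trial.

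**The case against.** The strongest case on the other side has five parts.

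- **The design is declared.** The study is titled a pilot and calls itself open-label. This is true, but it does not explain why the assessor must know the arm. The tests are outside standard care and dosing sits with the post-transplant team, so the tester has no evident need for that knowledge.
- **Some safeguards exist.** Coordinators are trained to a standard, MOCA and DSS are available on paper or as an app, and a study ID is assigned at entry. These narrow the scope for examiner influence on MOCA and DSS. None of them masks anyone, and they do little for the CGI.
- **A new week-6 rater could harm the CGI.** This stands. The CGI rates change, and the protocol names no baseline tremor severity score. A masked rater who never saw the patient at baseline would add error. Masking should therefore keep the same person at both visits.
- **Staffing is not documented.** This also stands. Section 7 uses a plural, and Section 3 speaks of "research coordinators, biostatisticians and other research services available", which describes the campus and not staff assigned to this trial. The number of coordinators and their other duties are not given.
- **The magnitudes are illustrative.** This is correct. The documents give no bias size and no SD, and there is no reason to expect the same shift on an impression scale as on a performance test.

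A reader might infer two stronger claims. One is that coordinators rate all the primary outcomes. The text says only that they administer the tests; the PGI is the patient's rating and the CGI scorer is unnamed. The other is that masking the week-6 assessor would remove most of the bias. Nothing in the documents supports that, because patients know their arm and the share of bias due to the assessor is unknown.

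**Conclusion.** The point holds in a limited form. The protocol masks no assessor and names no CGI rater, so following it as written leaves the week-6 CGI, and the administration and scoring of MOCA and DSS, open to assessor expectation that the t test cannot separate from a drug effect. This is more than a missing detail, because it affects the primary endpoint and cannot be repaired after the data are collected.

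The size is unknown. The figures of about 12%, 21% and 48% apply to one test, with 30 per arm, a two-sided 5% level, no true effect and assumed shifts of 0.2, 0.3 and 0.5 SD. They show that modest shifts matter at this sample size, and no more than that. That the shift would favour Envarsus is plausible given the stated hypothesis, but it is not established. The change is worth making before week-6 testing; the sample size, tests and visits stay as they are.

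**What to change.** Add one paragraph to Section 7:

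1. Name the role that scores the CGI, and state whether that person knows the arm.
2. Where existing staffing allows, have the same coordinator test a given patient at baseline and at week 6. Keep that coordinator out of randomisation, conversion and dosing for that patient, and do not tell them the arm.
3. Ask patients not to mention their drug until testing is over.
4. Score the MOCA and DSS sheets under study ID, without the arm. This is still useful if item 2 cannot be met.
5. Record each instance of unmasking.
6. State in the conclusion that these steps reduce assessor bias only: PGI, OTSWI and QUEST, and patient expectation or effort on MOCA and DSS, remain unmasked.

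The cost is visit scheduling and one protocol paragraph. Some accidental unmasking will occur. The arrangement depends on at least one other team member handling allocation, and the sponsor must confirm this because the number of coordinators is not given.

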Our research aims to focus on the neurocognitive effects of Envarsus ® versus tacrolimus immediate release. There is a correlation between peak levels of tacrolimus and CNS toxicities such as tremor⁷. As previous studies have shown that elderly patients experience higher trough levels of tacrolimus and are more sensitive to the effects of medications, they experience higher occurrence and severity of such medication related toxicities^{5,6}. Therefore, it is our hypothesis that by transitioning patients from tacrolimus immediate release to Envarsus ® we will eliminate the peak-dose effect and see a significant decrease in toxicities in the older patient population.

References

- 1. Kostro, J,Hellmann, A et al. "Quality of life after kidney transplantation: a prospective study". Transplant Proc. 48.1 (2016): 50-54.
- 2. Weber, M, Faravardeh, A et al. "Quality of Life in Elderly Kidney Transplant Recipients." *The American Geriatrics Society*. 62 (2014):1877-1882.
- 3. Tacrolimus. Lxi-Drugs. Lexicomp. Wolter Kluwer Health, Inc. Riverwoods, IL. Accessed July 19,2017.
- 4. Prograf® [package insert]. Northbrook,IL: Atellas Pharmaceuticals 2005.
- 5. Klotz, U. "Pharmacokinetics and drug metabolism in the elderly"41.2(2009):67-76.
- 6. Jacobson, P and Schaldt, D et al. "Lower Calcineurin Inhibitor Doses in Older Compared to Younger Kidney Transplant Recipients Yield Similar Troughs." *American Journal of Transplantation* 12 (2012):3326–3336

4) Inclusion and Exclusion Criteria

Inclusion Criteria:

- 1. Recipient of a kidney transplant
- 2. Age 65 or greater at the time of transplant
- 3. Kidney graft is functional (not dialysis dependent) by 4 weeks post-transplant
- 4. Have IR tacrolimus as maintenance therapy
- 5. Have BMI < 35 at time of transplant
- 6. Achieve therapeutic tacrolimus level within 4 weeks post-transplant

Exclusion Criteria:

- 1. Recipient of a simultaneous non-kidney transplant (pancreas)
- 2. Had an episode of rejection before study enrollment
- 3. Had a TIA/CVA after transplantation and before study enrollment
- 4. Had a neurologic injury after transplantation and before study enrollment
- 5. Blindness
- 6. Have an mTOR inhibitor as maintenance therapy

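### The primary tremor scales rate change in tremor, but entry does not require tremor and the analysis ignores baseline tremor, so any benefit is diluted in proportion to the share of patients who have tremor

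*Combined protocol and SAP*

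**What the plan says.** Section 6 (Study Endpoints) makes tremor one of three primary measures: "Change in neurocognitive side effects assessed by MOCA scale, Digit symbol substitution test and tremor assessment scale". Section 7 (Procedures Involved) lists the tests, introduced by "Below are the neurocognitive tests that we will perform on each patient". Item 3 of that list, Tremor Assessment, consists of a patient and a clinician global impression rating, and "Both are 7-point scales assessing tremor change". The response categories are not given.

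Section 7 supports the choice by the scales' use in an earlier switching study. The reference list gives that study's title, which begins "Switching Study of Kidney TRansplant pAtients with Tremor".

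Section 4 has six inclusion and ten exclusion criteria, and none mentions tremor. The nearest is "Have IR tacrolimus as maintenance therapy".

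The only tremor rate is in Section 3 (Background), from a package insert: "about one-third of patients experience tremors and one-fourth of patients experience headaches". The same section says that those studies had a mean age of 48 years (range 17 to 77), and argues that older patients have more frequent and more severe toxicity. It gives no tremor rate for patients aged 65 or more.

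The data analysis plan in Section 8 says the sample size was calculated to "detect a 1 point difference for each neurocognitive test we plan to use", with the arms compared by a two-sample t test. It gives no SD, alpha or power. It also gives no tremor subgroup, no stratification by tremor and no rule for scoring patients without tremor.

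**The concern.** A change rating can show improvement only in a patient who has something to improve. The scales were taken from a study of patients with tremor into a trial that admits patients with or without it. Those without tremor can rate only no change or worse. Their ratings enter the t test with the same weight as those of patients who can respond.

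The stakes are mainly in interpretation. A null tremor result over all patients could be read as no effect of Envarsus on tremor, when an unknown and possibly large share had none to reduce. The 1-point target is also hard to interpret, because what it demands of tremulous patients depends on a tremor share that the plan does not state.

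**Working it through.** **The plan's own figure.** Section 7 plans 30 patients per arm. With no SD, alpha or power stated, this can only be solved backwards. For a 1-point difference, SD = sqrt(30/2) / (z_alpha + z_power).
- Two-sided 5%, 80% power: 3.873 / 2.802 = 1.38. At 90% power: 1.20.
- One-sided 5%: 1.56 (80% power) and 1.32 (90% power).

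The figure of 30 can be neither confirmed nor refuted for the tremor scales.

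**What 1 point requires.** Inputs:
- Target difference of 1 point (Section 8).
- Tremor share p: one-third from Section 3; the other values are assumptions.
- Largest improvement of 3 steps. This assumes no change is the middle of the seven categories.
- IR arm unchanged and no new tremor in either arm (assumptions).

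The arm difference is p x g, where g is the mean gain in tremulous Envarsus patients. The largest possible difference is 3p, and the gain needed for 1 point is 1/p.

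| Tremor share p | Largest arm difference (3p) | Mean gain needed (1/p) |
|---|---|---|
| 1/4 | 0.75 | 4.0 (not attainable) |
| 1/3 | 1.00 | 3.0 (the maximum) |
| 1/2 | 1.50 | 2.0 |
| 2/3 | 2.00 | 1.5 |
| 1 | 3.00 | 1.0 |

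At one-third, a mean gain of 2 steps gives an arm difference of 0.67, and 1 step gives 0.33.

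**If tremor appears or worsens on IR.** Take p = 1/3 and suppose that new tremor of 1.5 points arises in 20% of IR and 5% of Envarsus patients who had none. This adds (2/3) x (0.20 - 0.05) x 1.5 = 0.15 point to the difference. The gain needed falls to (1 - 0.15) / (1/3) = 2.55 steps.

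**Power.** The SDs, benefits and new-tremor rates below are illustrative; none is in the documents. Let d be the benefit in tremulous patients, with SD 1.2 in them and 0 to 0.5 in the others. Variance in the Envarsus arm is p(1.2² + d²) + (1-p)s² - (pd)², and in the IR arm p(1.2²) + (1-p)s², where s is the SD in patients without tremor.

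For p = 1/3, d = 1.5 and s = 0, the variances are 0.98 and 0.48. Their mean is 0.73, so the SD is 0.85. The difference is 0.5 point and power at 30 v 30 is 61%; with s = 0.5 it is 52%. The tremulous subset alone (about 10 v 10) has 75%. For d = 1.0 the figures are 31-38% over all patients and 42% in the subset.

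Simulation with p = 1/3, SD 1.2, s = 0 and d = 1.5, with the tremor count varying by chance:

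| New tremor, IR v Envarsus | Plain t test, all | Adjusted for baseline tremor, all | Tremulous subset only |
|---|---|---|---|
| none | 63% | 72% | 73% |
| 20% v 5% (1.5 points worse) | 76% | 85% | 72% |

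For d = 1.0 with new tremor of 20% v 5%, the plain t test has about 55-57% and the subset 41%.

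Power depends strongly on the assumed spread. With whole-step gains averaging 1 step and less spread in tremulous patients, a separate simulation of the plain t test detected the same 0.33-point difference in about 65-86% of runs, not 31-38%.

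**The case against.** The strongest case is that the one-third figure is misapplied. It is an adverse-effect rate from a population with mean age 48, not the prevalence at enrolment among recipients aged 65 or more, and the protocol itself expects more toxicity in the elderly. At one-half or two-thirds the largest possible difference is 1.5 or 2.0 points, above the target. The trial also compares arms, so worsening or new tremor on IR adds to the difference. The three-step layout is an assumption, because the categories are not in the documents. All of this stands. A reader might infer that 1 point is the ceiling of the scale in this trial, but the documents do not support that as a general statement.

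A reader might also infer that the tremor comparison has no useful power. That does not follow: patients fixed at no change reduce the spread as well as the mean, and the power figures vary widely with SDs that the plan does not give.

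A third inference would be to restrict the primary tremor analysis to patients with baseline tremor. That is a trade-off. It discards new tremor and lost power in the simulations once new tremor on IR was allowed (72% against 76% for the plain t test at a 1.5-point benefit).

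Finally, an all-comer population is legitimate for a 60-patient pilot on side effects in elderly recipients. MOCA and DSS are unaffected, and QUEST adds tremor-specific self-report. This limits the reach of the point. It does not answer the dilution in the primary tremor measure, because QUEST is not part of the primary endpoint.

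**Conclusion.** The concern holds as a problem of dilution and interpretation. The documents establish that tremor is a primary measure, that it is assessed only by change ratings, that entry does not require it, and that the planned t test ignores it. Any benefit in tremulous patients is therefore multiplied by the tremor share before it reaches the arm difference.

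The exact requirements (3.0, 2.0 and 1.5 steps at shares of one-third, one-half and two-thirds) rest on a centred scale, an unchanged IR arm and no new tremor. The share in this population is unknown. The case for change does not depend on one-third being right: in the simulations, adjusting for baseline tremor in all patients matched or beat the planned t test in every scenario tried. The plan should be changed, and the change is small.

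**What to change.** 1. Before randomisation, record tremor as present or absent by a stated rule, using the baseline tremor assessment and questionnaires already planned. The rule must be written: PGI and CGI rate change and have no earlier state to refer to at baseline, and the protocol gives no tremor cut-off for QUEST.
2. Stratify the randomisation on this factor.
3. Keep all patients in the tremor comparison, so that new tremor counts, but replace the plain t test with a model containing arm and baseline tremor status.
4. Prespecify and report the arm difference in patients with baseline tremor, and the count of new or worsened tremor in the rest. A null all-patient result should not be reported as no effect on existing tremor.
5. Restate the 1-point tremor target with its assumed tremor share and SD, and state the scale categories.

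MOCA and DSS need no change on this account.

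The cost is protocol wording, one stratification factor and one present/absent rule, with no added visit or test. The subset estimate will be imprecise: at one-third prevalence it rests on about 10 v 10 patients (30 x 1/3 per arm).
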